UCSF Headache Center
Protocol

NCT0366663

Sphenopalatine Ganglion (SPG) Block Randomized Placebo Controlled Study

11/29/2018
Version 1.6

[name]
Department of Neurology
UCSF Headache Center
[name]
[name]
[contact]
[contact]

CONFIDENTIAL

Table of Contents:

- 1) Introduction
 - a) Project summary
 - i) Name and dosages of drugs
 - ii) Pharmaceutical class of drugs
 - iii) Structural formula of drugs
 - iv) Route of administration
- 2) Research Plan and Procedures
 - a) Hypothesis
 - b) Aims
 - c) Study Design
 - d) Background and significance
 - e) Preliminary studies
 - f) References
- 3) Procedure
 - a) Study drugs
 - b) Inclusion and exclusion criteria
 - c) Recruitment and Consent
 - d) Risks and Benefits
 - e) Data collection
 - f) Safety monitoring

1. Introduction

a. Project summary :

Chronic Migraine is a brain disorder with high prevalence. It is the 7th leading cause of disability worldwide according the WHO.

SPG block is a treatment for migraine that has been used for two decades. It can be done by needle injection of anesthetic to the region of the SPG. However, there are now multiple catheter devices that can be used to non-invasively administer anesthetic topically through the nasal cavity to the region of the SPG where the anesthetic is then absorbed through thin membranes covering the SPG.

Various anesthetic agents have been studied however currently, to our knowledge, there is no head to head comparison of the long versus short acting anesthetics. Studies of SPG blocks in the setting of chronic migraine are few as compared to the use of SPG as acute treatment for migraine.

With the use of an RCT, we aim to determine the overall efficacy of SPG blocks used at longer intervals than have been studied in the past as compared to placebo, as well as to examine the relative efficacy of the anesthetics used most commonly and studied for SPG blocks.

We will be using an FDA cleared device, the Sphenocath which was developed and registered with the FDA for this specific population and purpose. The study intervention is the standard practice in the UCSF Headache Center to perform SPG blocks for our patients with chronic migraine. The frequency we plan is less often than in previous studies of this intervention in this population. Patients will continue their usual headache care and treatments during the study.

i. Name and dosage of drugs

- a. 2% lidocaine, 0.5cc each nostril
- b. 0.25% bupivacaine, 0.5cc each nostril
- c. 0.5% ropivacaine, 0.5cc each nostril
- d. Placebo (normal saline), 0.5cc each nostril

ii. Pharmaceutical class of drugs

Anesthetics

iii. Structural formula of active drugs

- a. lidocaine : $C_{14}H_{22}N_2O$
- b. bupivacaine : $C_{18}H_{28}N_2O$
- c. ropivacaine : $C_{17}H_{26}N_2O$

iv. Route of administration

- 1. Nasal application, via Sphenocath. This device is a small, flexible catheter which is a needle-less, topical applicator. It is FDA cleared for use to deliver anesthetic solution to the region of the SPG.

2. Research Plan and Procedures

a. Hypothesis

Use of SPG (sphenopalatine-ganglion) blocks approximately every 2-4 months for three treatments will be proven superior in migraine headache treatment as compared to placebo.

Using a placebo group and randomized control study design will control for the natural waxing and waning variation that can be expected to occur in migraine over the study duration.

Headache frequency and severity, as measured by daily standard headache diary, will improve with the use of repeated SPG Blocks every 2-4 months by the end of the study period.

One of the anesthetics will be found to be more efficacious than the other.

There will be an improvement in the effect and duration of the therapeutic benefit of the each of the repeated SPG blocks with anesthetics over time.

Patients receiving active treatment will require fewer acute treatments and emergency room visits than those receiving placebo.

b. Aims

- i. To determine whether the use of SPG (sphenopalatine-ganglion) blocks less frequently than previously studied will still be effective in migraine headache prevention.
- ii. To determine if there is a difference in efficacy between lidocaine and bupivacaine and ropivacaine
- iii. To determine whether the repeated use of SPG blocks every 2-4 months for 3 treatments will have a cumulative effect with subsequent

- treatments providing better and longer lasting effects on headache frequency and severity.
- iv. To determine if repetitive SPG blocks can reduce the need and use of acute treatments and emergency room visits

c. Study Design

This will be a randomized, double blind, placebo controlled study of non-invasive SPG blocks in patients with chronic migraine using the Sphenocath device.

Approximately 120 patients will be randomized in a 1:1:1:1 ratio to receive SPG block using lidocaine, or bupivacaine or ropivacaine or normal saline every 2 to 4 months for three treatments. There will be approximately 30 subjects in each group.

The study period will run approximately 8 months.

During the study period participants will continue to use their usual headache medicines and treatments. Participation in this study will not change their other headache treatments.

d. Background and significance

The sphenopalatine ganglion is located in the pterygopalatine ganglia close to the sphenopalatine foramen and is located below the maxillary nerve as it crosses the fossa. The sphenopalatine ganglion has multiple connections to facial, trigeminal, parasympathetic and sympathetic systems which make it a promising target for migraine treatment. (1,2,3)

SPG blocks are widely used as an acute treatment of migraine⁽⁴⁻⁷⁾ ; and other headache disorders⁽⁸⁻¹⁰⁾ although the preventive effects⁽¹¹⁾ have not been widely studied .

SPG blocks are quite commonly performed at the headache center to treat chronic migraine, and patients report significant relief. We would like to determine if the frequency and medications that we use as our standard of care prove to be significantly better than placebo and also to see if there is a difference in the anesthetics that we usually instill.

e. Preliminary studies

The use of SPG blocks for head pain goes back over a century. Sluder in 1908 was the first to describe injection of the sphenopalatine ganglion via the nasal approach and subsequently reported success with its use in headache, facial neuralgia, earache, and “lower-half headache”. (12)

Intranasal (IN) instillation of lidocaine has been studied as an acute treatment for migraine both in the emergency department and in the home setting. (13-16).

Maizels and Geiger (1999) in their placebo controlled study trained patients to self-administer the study solution intranasally (either 4% lidocaine vs placebo) (13). Fifty one subjects were instructed to treat every headache for 1 month. There were 95 headaches treated with IN lido and 108 headaches with placebo. Headache relief at 15 minutes was found to be markedly superior to placebo.

Benefit of SPG blocks with various anesthetics has been shown to be helpful in other head pain syndromes including reducing pain atypical face pain and cluster headache. (8-10)

In migraine specifically, SPG blocks have been studied in various populations including acute migraine, chronic migraine, chronic migraine with medication overuse, and status migrainosus. (4-7,11)

There are various methods for performing SPG blocks some of which are more invasive and risk prone than using catheter application.

Suprazygomatic injections to the region of the SPG was studied as an acute migraine treatment by Mehta et al (2018) in a cohort study (4). They injected a mixture of steroid (dexamethasone) and 0.5% ropivacaine through the skin above the zygomatic arch, to the region of the SPG. Eighty eight patients received a total of 252 injections to block the SPG. They reported no significant complications of the procedure. At 30 minutes following treatment, the overall reduction of pain among patients was statistically significant.

Cady et al (2015) investigated a less invasive, novel device (Tx360), to perform SPG blocks for chronic migraine. (7) They performed a double-blind, parallel-arm, placebo-controlled, randomized trial of 38 patients. They measured pain scores at baseline, 15 minutes, 30 minutes, and 24 hours post treatment. The active phase consisted of a series of 12 SPG blocks with 0.5% bupivacaine or saline which were provided 2 times

per week for 6 weeks. All side effects were mild to moderate, short in duration, and resolved spontaneously. No subject withdrew because of side effects which included mouth numbness (18%), lacrimation (29%), and bad taste (15%). Patients treated with bupivacaine showed a significant reduction in their pain scores from baseline at all intervals. Headache Impact Test-6 (HIT-6) scores were statistically significantly decreased in subjects receiving treatments with bupivacaine from before treatment to the final treatment, whereas no significant change was seen in the placebo group.

The authors went on to analyze the long term effect of these repetitive SPG blocks with bupivacaine in the second part of their study (11). They reassessed patients at 1 month and 6 months post active treatment and they found a sustained reduction of headache days along with an improvement in functional assessment in the treatment group.

- a. Study drugs : bilateral nasal applications via Sphenocath (each consisting of 0.5 cc of liquid per nostril) of the following:
 - i. Lidocaine 2% OR
 - ii. Bupivacaine 0.25% OR
 - iii. Ropivacaine 0.5% OR
 - iv. Normal Saline
- b. Inclusion and exclusion criteria

Inclusion Criteria

1. Age 18 years or more at time of consent
2. Current patients in the UCSF Headache Center eligible to receive SPG blocks for migraine and would otherwise receive treatment clinically
3. Ability to provide consent for the research study

Exclusion Criteria

1. Pregnant or breast feeding within 4 weeks of enrollment

2. Inability to communicate with the study team
3. Patients who cannot read and understand English
4. Deemed unsuitable for enrollment in study by the investigator
5. Allergy to local anesthetics or saline

c. Recruitment and Consent

The patient will come to the UCSF Headache Center for their regular clinic appointment.

During this visit, the study team member will describe the research study and if they are interested in participating, the patient will have time to read through the consent form and clarify any questions that the patient may have regarding the study.

Once the patient reads and understands the Informed Consent Form, eligibility will be determined by the study physician based on medical history and study criteria.

After signing the consent and HIPPA, they will be randomized to their study assignment.

d. Risks and Benefits

As part of the consent process, participants will be told that when topical anesthetics are used in the nose, mouth, or throat, it may cause decrease in local sensation for a few minutes. Participants will be told to be mindful when eating or drinking any foods or liquids in the hour after receiving treatment. They will be informed that they may experience short lasting dizziness or lightheadedness which is exceedingly rare in our experience but reported in previous studies.

The risk of allergies will be discussed, and all current medications and health conditions will be considered by the investigators before offering participation to patients.

Randomization and placebo risks will be described to the participant during the consent process.

e. Data collection

The data collected at each study visit will be the frequency and intensity of migraine headaches during the interval period. Data will be stored in HIPAA compliant fashion.

Chi square will be used to analyze to determine if there is a significant statistical difference among the groups.

After the next routine clinic visit post study period, we will compare mean number of headache days per month of mild, moderate and severe headache post treatment to the baseline collected prior to first SPG block.

f. Safety monitoring

Although there is safety data for the use of anesthetic nasal blocks, and a DSMB is not required, safety will be carefully monitored throughout this study.

There is no planned interim analysis. Participants may be removed from the study if it is in their best interest and it will be up to the determination of the PI, or participant.

Any serious adverse events will be communicated to the IRB, in accordance with their guidelines.

All serious and non-serious adverse events will be collected in an adverse event reporting form.

In accordance with the standard operating procedures and policies of the local Institutional Review Board (IRB), the site investigator will report SAEs to the IRB per UCSF IRB guidelines.

As part of the participant's visits, we will ask the patient about frequency and intensity of their headaches between visits (and review their standard clinic headache diary). Home medications along with any new medical problems will be reviewed with the participant before receiving the study treatment.

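### Earlier SPG blocks are neither recorded nor used in the analysis, so the within-arm change from baseline and the cumulative-effect aim may be hard to interpret

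*Combined protocol and SAP*

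**What the plan says.** Section 3.b of the protocol admits "Current patients in the UCSF Headache Center eligible to receive SPG blocks for migraine and would otherwise receive treatment clinically". The five exclusions end with "Allergy to local anesthetics or saline"; none concerns an earlier SPG block.

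The source clinic uses the intervention routinely. Section 1.a states: "The study intervention is the standard practice in the UCSF Headache Center to perform SPG blocks for our patients with chronic migraine". Section 2.d adds: "SPG blocks are quite commonly performed at the headache center to treat chronic migraine, and patients report significant relief". Section 2.e says that the clinic has used this device for more than 2 years and uses all three study anesthetics as a matter of routine.

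Section 3.e lists headache frequency and intensity as the visit data, names a chi-square test among groups, and compares post-treatment headache days per month with the "baseline collected prior to first SPG block". It does not say whether that is the first study block or the first ever. Section 3 describes 1:1:1:1 randomisation in blocks and names no stratification factor. Section 3.c uses medical history to decide eligibility, and section 3.f has home medications and new medical problems reviewed at visits. Neither makes prior SPG blocks an analysis variable. Section 1.a also states: "Patients will continue their usual headache care and treatments during the study".

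Aim iii in section 2.b asks whether successive blocks work better and last longer. On persistence, section 2.e reports of an earlier bupivacaine trial: "They reassessed patients at 1 month and 6 months post active treatment and they found a sustained reduction of headache days".

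**The concern.** Patients drawn from a clinic that gives these blocks routinely may include some who have already had one, perhaps recently. The plan itself supposes that benefit can last: it spaces study blocks months apart and cites a sustained reduction after an earlier course. If benefit from an earlier block is still present when baseline is taken, that baseline is lower than it would otherwise be. A participant on active drug then has less room to improve, and a participant on saline may appear to worsen as the earlier benefit fades.

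Two results are exposed. One is the post-versus-baseline comparison in section 3.e, a within-arm quantity that randomisation does not protect. The other is Aim iii: if blocks accumulate in effect, a study block counted as the first may really be a later one, and the number of earlier blocks is needed to read the result. Without a record of prior exposure, neither problem can be examined afterwards.

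**Working it through.** **The plan's own figure.** Section 2.c gives about 30 subjects in each of four groups: 4 × 30 = 120, which agrees with the stated total. No alpha, power, effect size or SD is given, so the sample size cannot be derived.

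**Inputs that must be assumed.** The documents give neither the share of participants with an earlier block nor the amount of benefit left at baseline.
- True block effect: -3 headache days per month.
- f: share previously treated.
- c: share of the block effect still present at baseline in those participants.
- r: share still present at follow-up in those on saline.
- A study block brings previously treated and untreated participants to the same level. If Aim iii's cumulative effect is real, this would not hold exactly.

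**Within-arm change, earlier benefit gone by follow-up on saline (r = 0).** Mean baseline is shifted by -3fc in every arm.
- Active change = -3 - (-3fc) = -3(1 - fc)
- Saline change = 0 - (-3fc) = +3fc
- Active minus saline = -3(1 - fc) - 3fc = -3

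| f | c | Active change | Saline change | Difference |
|---|---|---|---|---|
| 0.10 | 0.5 | -2.85 | +0.15 | -3 |
| 0.10 | 1 | -2.70 | +0.30 | -3 |
| 0.25 | 0.5 | -2.625 | +0.375 | -3 |
| 0.25 | 1 | -2.25 | +0.75 | -3 |
| 0.50 | 0.5 | -2.25 | +0.75 | -3 |
| 0.50 | 1 | -1.50 | +1.50 | -3 |

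The within-arm changes move with f and c. The randomised difference does not.

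**First exception: carry-over lasting into follow-up on saline.** Saline change becomes 3f(c - r), so the difference is -3(1 - fc) - 3f(c - r) = -3(1 - fr). At f = 0.5 this is -2.625, -2.25 and -1.5 days for r = 0.25, 0.5 and 1. For scale, assume 80% power for one pairwise comparison at two-sided 5% with 30 per arm, which corresponds to (1.960 + 0.842) × √(2/30) = 0.72 SD. Power = Φ(2.802(1 - fr) - 1.960), which at f = 0.5 gives 69%, 56% and 29% for the same three values of r.

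**Second exception: chance imbalance.** Suppose an active arm has 6 of 30 (0.20) more previously treated participants than saline. With r = 0, the difference in change becomes -3 + 3c × 0.20, a shift of 0.3 day at c = 0.5 and 0.6 day at c = 1. In a simulation of unstratified allocation (independent binomial draws, 30 per arm), the chance that at least one active arm differs from saline by 6 or more previously treated participants, in either direction, is 24% at f = 0.25 and 35% at f = 0.50.

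**The case against.** The strongest reply is that this is a randomised, placebo-controlled trial whose leading hypothesis is superiority to placebo, and section 2.a says that the placebo group is there to control for change over time. The arithmetic bears this out: with carry-over at baseline only, the active-minus-saline difference is untouched in expectation. That stands. A reader might infer that the placebo comparison is diluted, or that half of the treatment effect disappears. The documents do not support either as a general statement. The halving concerns only the within-arm change, at f = 0.5 and with the whole earlier effect present at baseline.

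Other tempting readings also go too far:
- *Participants already receive blocks.* Section 3.b requires eligibility for blocks, not past use. Read literally, section 3.e's baseline could even mean before the first block ever, although no criterion enforces that. Enrolment of previously treated patients is possible, not stated.
- *The plan treats baseline as untreated.* It does not say so, and it keeps usual headache care going throughout.
- *Benefit lasts 6 months.* The cited result followed 12 bupivacaine blocks in 6 weeks with another device. The documents give no such persistence for blocks 2 to 4 months apart, so a 6-month cut-off has no support for this schedule.
- *Experienced participants recognise saline.* Nothing in the documents ties this to prior users. Section 3.c–d consent information about reduced sensation goes to everyone.
- *Stratification and placebo contrasts by stratum are required.* Adjustment is an accepted alternative to stratification. At f = 0.25 a stratum contrast has about 7.5 previously treated participants per arm (30 × 0.25), with a detectable difference at 80% power of 2.802 × √(2/7.5), about 1.4 SD. At f = 0.10 there are 3 per arm.

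What remains after these concessions is the unrecorded exposure, the undefined baseline block, and their effect on the within-arm change and Aim iii.

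**Conclusion.** The point holds in a limited form. The protocol allows previously treated patients to enter, does not list their prior exposure as data, and does not use it. The stated change from baseline can therefore understate the effect of starting treatment, and saline can appear to worsen. Under an assumed 3-day effect with f = 0.5, the active arms would retain 75% (c = 0.5) or 50% (c = 1) of the true change; at f = 0.10 they would retain 95% or 90%. These sizes rest wholly on assumed values of f and c.

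The randomised comparison remains sound in expectation. It is weakened only if earlier benefit lasts into follow-up on saline, or if prior exposure happens to be unbalanced, which is plausible at about 30 per arm. Aim iii cannot be interpreted with confidence without the number of earlier blocks. This is a cheap and worthwhile improvement, not a flaw that invalidates the placebo contrast.

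**What to change.** In section 3.e:
1. State that the first SPG block means the first study block.
2. Record from the clinic chart, at enrolment, the number of prior SPG blocks and the date of the last one.
3. Log any SPG block given outside the study, since usual care continues.
4. Base efficacy conclusions on the between-arm comparison of headache days, adjusted for baseline headache days and prior SPG exposure.
5. Label any results by prior exposure as descriptive only, and do not read the within-arm change as the effect of starting treatment.

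Stratifying the existing block randomisation by prior SPG block (yes or no) is an optional alternative. It would add a second randomisation list and a few incomplete blocks.

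The cost is one chart item, a simple log of outside blocks, one covariate, and a regression model in addition to the chi-square test that the plan names. Eligibility, recruitment and care do not change.

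### Mild-only and moderate-only headache days have no fixed direction of benefit, and one pooled count would miss a pure fall in severity; nested cumulative counts would avoid both problems

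*Combined protocol and SAP*

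**What the plan says.** Section 2.a (Hypothesis) makes a claim with two parts: "Headache frequency and severity, as measured by daily standard headache diary, will improve with the use of repeated SPG Blocks every 2-4 months". The third aim in section 2.b again names both parts, looking for later "treatments providing better and longer lasting effects on headache frequency and severity".

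Section 3.e (Data collection) says: "The data collected at each study visit will be the frequency and intensity of migraine headaches during the interval period". It defines no intensity scale or summary.

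The analysis text in 3.e has two sentences. One gives the test: "Chi square will be used to analyze to determine if there is a significant statistical difference among the groups". It attaches no outcome variable, category or direction to that test. The other gives the only comparison in the analysis text that names its variable, the "mean number of headache days per month of mild, moderate and severe headache post treatment to the baseline" taken before the first block. It does not say whether the three grades are separate outcomes or parts of one total, which direction is benefit for each grade, or which result decides.

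**The concern.** A day that goes from severe to moderate, or from moderate to mild, is a better day. In separate counts it leaves one grade and is added to the next lower one. Mild days can therefore rise because moderate days became milder, which is benefit, or because headache-free days became mild, which is harm. The mild count alone cannot tell these apart. Moderate days have the same problem, and can also look flat when inflow from severe and outflow to mild nearly cancel.

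If the sentence instead means one total, a shift in grade with no change in the number of headache days is invisible, and the severity part of the hypothesis has no test.

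What is at stake is how the result is read. One arm can show mild days up and severe days down, and the plan has no rule fixed in advance for weighing the two.

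**Working it through.** **Figures in the plan.** The protocol gives no power, effect size, standard deviation or baseline distribution of headache days, so there is no planning figure on this point to reproduce. The one check available, 120 / 4 = 30 per arm, agrees with section 2.c. All day counts and shift shares below are assumptions.

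**Set-up.** Let m, d and s be baseline mild, moderate and severe days per month. Let a be the share of severe days that become moderate, b the share of moderate days that become mild, and c the share of mild days that become headache-free. No day gets worse. Then:

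- change in mild = b·d − c·m (either sign)
- change in moderate = a·s − b·d (either sign)
- change in severe = −a·s (never rises)
- change in total = −c·m (never rises; does not depend on a or b)
- change in moderate-or-severe = −b·d (never rises; does not depend on a)

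Mild days rise whenever b·d exceeds c·m, and moderate days rise whenever a·s exceeds b·d. This follows from the definitions and needs no outside data.

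**Example 1, severity only.** m = 5, d = 8, s = 7; a = b = 0.5; c = 0.

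- Severe: 7 − 3.5 = 3.5 (−50%)
- Moderate: 8 − 4 + 3.5 = 7.5 (−6%)
- Mild: 5 + 4 = 9 (+80%)
- Total: 20, unchanged (0%)
- Moderate-or-severe: 15 to 11 (−27%)

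**Example 2, severity and frequency.** Take Example 1 and remove a quarter of the days in every grade (multiply by 0.75).

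- Mild 6.75 (+35%), moderate 5.625 (−30%), severe 2.625 (−63%)
- Total 15 (−25%); moderate-or-severe 8.25 against 15 (−45%)

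Mild days are up by about a third although a quarter of headache days have gone.

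**Example 3, severe to moderate only.** a = 0.5, b = c = 0 gives 5/11.5/3.5. Severe falls 50% and moderate rises by 3.5 days, while moderate-or-severe stays at 15 and the total at 20. Of the three cumulative counts, only severe days show this benefit.

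**Range.** Four assumed baselines (none/mild/moderate/severe: 10/5/8/7, 12/4/6/8, 10/10/6/4, 10/3/5/12) were crossed with five sets of shares (a, b, c): (0.3, 0.3, 0.3), (0.5, 0.3, 0.2), (0.4, 0.4, 0), (0.2, 0.2, 0.5), (0.5, 0.2, 0.2). All 20 combinations are improvements.

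| Count | Change, days per month | Rose in |
|---|---|---|
| Mild | −3.8 to +3.2 | 13 of 20 |
| Moderate | −0.8 to +5.0 | 14 of 20 |
| Severe | −6.0 to −0.8 | 0 of 20 |
| Moderate-or-severe | −3.2 to −1.0 | 0 of 20 |
| Total | −5.0 to 0.0 | 0 of 20 |

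The total was exactly 0.0 in all four combinations with c = 0.

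**The case against.** The strongest reply is that three graded counts lose nothing at the level of group means. Means add, so anyone given the three can form the total and the moderate-or-severe count. Severe days speak to severity and the sum speaks to frequency, and both have a fixed direction. Naming the three grades also makes the three-count reading the more natural one, so the pooled problem rests on the less likely reading. All of this stands, and it limits the point.

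Three stronger conclusions are tempting, and the documents do not support them.

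- A reader might infer that the stated measure gives a wrong or empty answer on severity under either reading. Under the three-count reading the severe count is informative.
- A reader might infer that the plan would score an effective block as worsening. No section says that a rise in mild days counts as worsening; the plan is silent on direction.
- A reader might infer that this sentence is where superiority to placebo fails. It is a comparison with baseline and mentions no arms. The comparison among groups is the chi-square sentence, which names no outcome. That gap is separate and wider than the choice of counts.

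The size also depends on the inputs: mild days fell in 7 of the 20 assumed combinations. What the reply does not remove is that two of the three named counts have no fixed sign under improvement, and that nothing in the plan says which count carries the conclusion.

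**Conclusion.** The point holds in a limited form. Mild-only and moderate-only days cannot serve as efficacy outcomes, because improvement can move them either way. Severe days and the total can, so the hypothesis on frequency and severity stays partly answerable under the three-count reading. Under the pooled reading, a pure fall in severity gives zero change.

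The direction result follows from the definitions. The sizes (+80%, −6%, −50% and 0% for mild, moderate, severe and total in Example 1) are illustrations on an assumed 5/8/7 baseline and are not predictions for this trial. The wording should be changed because a better set of outcomes is available from the same grades at little cost.

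**What to change.** In section 3.e, state the outcomes as nested cumulative counts per month, each with fewer days as benefit:

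1. headache days of any severity, for frequency;
2. moderate-or-severe headache days, for severity;
3. severe headache days, for severity.

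Grade each day by the worst grade recorded that day. Compare the change from baseline in these counts between arms. Report mild-only and moderate-only days descriptively and not as efficacy results. The third count must stay, because Example 3 shows that the first two alone can miss a halving of severe days.

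**Cost.** This is a wording change in 3.e. It assumes that the standard diary records a grade for each day, which the documents do not describe but which the present outcome already requires. Mild-only and moderate-only days stop being efficacy outcomes. The cumulative counts overlap, and the severity counts also fall when frequency alone falls: removing a quarter of days at every grade from 5/8/7 lowers moderate-or-severe days from 15 to 11.25 (−25%) with the mix of grades unchanged. They should therefore be read together with the total.

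### Removal is from the whole study with no outcome collection afterwards, so response-related removal would inflate improvement from baseline in every arm and shrink the active-placebo difference

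*Combined protocol and SAP*

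**What the plan says.** Section 3.f (Safety monitoring) states: "Participants may be removed from the study if it is in their best interest". The sentence goes on to say who decides: "it will be up to the determination of the PI, or participant". What the participant is removed from is the study, not the treatment. No section distinguishes the two, and none describes follow-up after removal.

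Section 3.e (Data collection) states what is recorded: "The data collected at each study visit will be the frequency and intensity of migraine headaches during the interval period". It then gives a chi-square test for a difference among the groups, with no time point attached. It sets the timing of the headache-day comparison as follows: "After the next routine clinic visit post study period, we will compare mean number of headache days per month". That comparison is against the baseline taken before the first block. No analysis set and no method for missing outcomes is stated.

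Three other statements bear on the point. Section 2.c describes the trial this way: "This will be a randomized, double blind, placebo controlled study of non-invasive SPG blocks". It also says of other care: "During the study period participants will continue to use their usual headache medicines and treatments". Under section 3.b, participants are patients who could have the block in routine care anyway.

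**The concern.** The headache-day comparison needs a value from after the study period, which runs about 8 months. A participant who leaves after the first or second treatment will not have that value unless someone goes on collecting it, and the plan tells nobody to do so.

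The loss matters most if it depends on how the participant is doing. That is plausible here. The center gives SPG block as standard practice, so a participant who is doing badly, with a one-in-four chance of saline, could leave and have an active block openly. A best-interest criterion is broad enough to cover such a case. Two things would follow. Those who remain would look better against their own baseline than the full arm does. If active treatment works, placebo would also lose more of its poor responders than the active arms do, which narrows the difference between arms. With about 30 per arm there is little precision to spare.

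**Working it through.** **The plan's own figure.** 4 arms × 30 = 120, which agrees with section 2.c. The 120 cannot be derived further, because alpha, power, effect size, SD and dropout are not given. Everything below is therefore an illustration on assumed inputs.

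**Assumed inputs.**
- Change in headache days per month: placebo N(-2, SD 6), active N(-5, SD 6). The true difference is -3 days, or 3/6 = 0.5 SD.
- 30 per arm, one active arm against placebo, two-sided alpha 0.05, normal approximation.
- One removal rule for both arms: probability of removal = 1/(1 + exp(-(a + b(x + 2)))), where x is the participant's change (higher is worse). The constant a is set so that 10%, 20% or 30% of placebo is removed.
- b = 0.3 or 0.1 per day. Per SD, the odds of removal multiply by exp(0.3 × 6) = 6.0 or exp(0.1 × 6) = 1.8.
- x is either the final change itself (correlation 1) or an earlier value with the same arm means and correlation 0.5 with the final one.

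**Formulas.** Mean among those remaining = arm mean + correlation × 6 × E(Z | not removed), where Z is the standardised x, found by numerical integration. Loss = 1 - (observed difference / -3).

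**Worked case** (b = 0.3, correlation 1, 20% of placebo removed). Removal in the active arm is 12%. The remaining means are -3.50 (placebo) and -5.93 (active). Difference = -5.93 - (-3.50) = -2.43. Loss = 1 - 2.43/3 = 19%.

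**All cases**, for 10% / 20% / 30% of placebo removed:

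| b | Correlation | Observed difference (days) | Loss of effect |
|---|---|---|---|
| 0.3 | 1 | -2.64 / -2.43 / -2.27 | 12% / 19% / 24% |
| 0.3 | 0.5 | -2.82 / -2.72 / -2.64 | 6% / 9% / 12% |
| 0.1 | 1 | -2.92 / -2.86 / -2.82 | 3% / 5% / 6% |
| 0.1 | 0.5 | -2.96 / -2.93 / -2.91 | 1% / 2% / 3% |

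**A harsher rule.** Suppose instead that every participant above a fixed interim cut-off is removed, taking the worst 10% to 30% of placebo, with interim-final correlation 0.5 to 0.7. A true 0.5 SD then becomes 0.35 to 0.45 SD. So 24% is the top of the graded-rule table, not a hard ceiling.

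**Comparison with baseline.** With b = 0.3 and correlation 1, the true placebo change of -2 appears as -2.8, -3.5 and -4.1. In the mildest row it appears as -2.2, -2.3 and -2.5.

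**No true effect.** If both arms have mean -2 and the same rule, both show the same inflated improvement and the difference between them is 0.

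**Power.** With everyone followed it is 0.49. In the first row of the table it is 0.42, 0.36 and 0.31. If removal is unrelated to outcome there is no bias, but with 27, 24 and 21 per arm power is 0.45, 0.41 and 0.37.

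**The case against.** A reader might infer that the PI removes poor responders and that the final comparison is then, by design, a biased completer analysis. The documents do not support that. The stated ground is the participant's best interest, in a safety section. Poor response is not named, and the participant may decide as well as the PI. The plan is silent on who is analysed, so it neither specifies completers nor discards data already collected.

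Nor is the post-study comparison the only analysis. The chi-square among groups is stated separately, and visit data on frequency and intensity exist up to the point of removal.

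Other features limit the harm. Blinding prevents removal from openly following the assigned arm, and usual headache treatment continues, which reduces the pressure to leave. The larger losses in the table need a steep rule that acts on the final outcome itself, which is not known when someone is removed. No false-positive risk between arms has been shown.

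All of this stands, and it makes the bias conditional and its size uncertain. It does not fill the gap. A common blinded rule still removes more placebo than active participants when the treatment works, and no text says that the earlier visit data will stand in for the missing final value.

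**Conclusion.** The point holds as a conditional one. Followed as written, removal ends outcome collection before the visit on which the headache-day comparison depends. If removal is related to response, improvement from baseline is inflated in every arm and the active-placebo difference is attenuated.

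The loss is about 2% to 24% over most of the graded scenarios, just over 1% in the mildest, and larger only under a sharp cut-off. These figures rest on an assumed SD, effect, removal rate and strength of association, none of which the documents give. The zero between-arm bias under no effect depends on the same blinded rule operating in all arms. If removal is unrelated to response, the cost is precision alone.

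This should be changed. Outcomes that were never collected cannot be recovered at analysis, and collecting them here is easy.

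**What to change.** Leave the decision about when a participant stops, and the participant's right to leave, as they are. Add to section 3.f that stopping study treatment does not by itself end study participation. Unless the participant withdraws consent to follow-up or to use of data, continue to record headache frequency and intensity at routine visits through the final time point. The source is already in use, since section 3.f has staff "review their standard clinic headache diary".

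Add to section 3.e that all randomised participants are analysed in their assigned arm using all available diary periods, for example in a likelihood-based repeated-measures model, with a sensitivity analysis for outcomes still missing. Record the reason for stopping while still blinded, and report reasons by arm.

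Cost: a sentence in section 3.f and a short analysis paragraph. The paragraph must also say how the model relates to the stated chi-square, which it would displace for headache days. Follow-up costs little, because these are existing clinic patients who keep a diary. The downside is that some off-treatment data, possibly including open-label block, enter the comparison and may dilute the estimate slightly.
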